4.0 Statistical Analysis Procedures

1.1 Data Quality

- 1.1.5 Data are assessed by the principal investigators for data quality across the study and the investigators will keep in close contact with each participant to assess correctness of reporting and data capture.
- 1.2.5 Participants reporting unusual changes in symptoms will be asked to report unusual activities that may impact values.

2.1 Power Calculation

2.1.5 As no prior study involving fasting and Long COVID exist, with the exception of two case reports, this trial's sample size was estimated based on the 2022 understanding of Long COVID and on publications at that time about Long COVID that had a nascent understand of the symptoms involved in the condition. The expected effect of fasting on Long COVID symptoms was estimated roughly to require 40 to 90 individuals per trial arm, in part depending on the severity of Long COVID symptoms experienced by those who would enroll.

3.1 Analysis Plan

- 3.1.5 The study population will be evaluated using an intent-to-treat approach to the statistical analysis. All subjects who have data regarding symptom severity scores available at each time point will be included in the analyses.
- 3.2.5 Demographics, anthropometric variables, risk factors, COVID-19 vaccinations, other medications, and socioeconomic variables will be described as percentages or means with standard deviations.
- 3.3.5 Symptom severity scores will be compared between the two study arms using the two-sided paired T-test at each time point, as appropriate. Based on the randomized design of the study, it is expected that most if not all of these data elements will be balanced between the TRE arm and the Fasting arm of the study. Similar comparisons will also be performed to compare between the treatment arms for changes at weeks 1, 2, or 3 of each treatment to examine potential timing of the impact of those interventions.
- 3.4.5 The presence of individual symptoms at baseline, end of the run-in period, end of Fasting, end of TRE, and end of the 10-week trial will be summarized with percentages or means. Examination of overall changes in all participants for LC-score and numLCsym will use two-sided Student's T-test to evaluate the differences in means at baseline and the end of the 2-week run-in phase, and at baseline compared to the final week of the trial. A repeated measures general linear model will be used to test differences between the two trial arms across baseline and the 10 end-of-week measurements of the LC-score and numLCsym.
- 3.5.5 Adherence to the Fasting intervention will be tracked for each participant using self-reported assessment of whether the components of the intervention were followed each week of the study and will be reported as percentages.
- 3.6.5 Adverse events and major adverse events will be recorded for each participant and reported as percentages along with counts of events at each time point.
- 3.7.5 Analyses will use R Studio.
- 3.8.5 Exploratory analyses will examine other features of the data set
- 3.9.5 Subgroup analyses may be conducted using non-paired two-sided t-tests to identify statistically significant correlations between mean percent decreases in the primary measures and various baseline characteristics.

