- 18. REDCap will send weekly reminders to subjects concerning when to start self-treatment A, when to start self-treatment B. Treatment group A, 'TRE then Fasting', has a low sugar diet and a 10-12 hour eating window. Treatment group B, 'Fasting then TRE', will have an 8 hour eating window with either a 36 or 60 hour water fast once a week.
- 19. FIRST FAST Subjects will be called after they complete the appropriate survey before their first water fast by a medical student volunteer or [name]. They will be informed of what to expect and reminded to take electrolytes. They will be reminded that they can STOP FASTING at any time. They will also be reminded of how to use the symptom flare-up form (via a public link) to talk to a med student and potentially have [name] call them. Per the new **First Fast Call Medical Student Instructions**, the medical student volunteers are expected to talk with subjects within 24 hours of receipt of a First Fast

email notification. Meanwhile, subjects are instructed not to start their first fast until after they have received their Pre-First Fast Call. If the medical student does not reach the subject, they leave a message with their cell phone number. They then must make at least two call attempts by 4 PST the day after the First Fast Call notification was received. All call attempts and their result will be documented in the subject's First Fast Call for m. As a backup, per the crossover emails, if the participant needs to start their first fast but has not been able to talk with a medical student by 7 pm EST, they may call [name]. [name] will check that the subject is indeed correct to initiate their fast at this time. He will then review the Fasting Safety procedures and update the First Fast Call instrument.

- 20. Survey reminders will be sent using the dateDiff function comparing today's date:time to the survey date of each participant's first Baseline Survey. If a subject misses a key survey, then they are considered withdrawn from the study. The first and third baseline surveys, the survey at the end of 4 weeks water fasting and the survey at the end of the relaxed time-restricted eating are considered key surveys.
- 21. If a subject wants to be removed from the study or no longer qualifies from the study, the subject will be removed, but the record will be maintained.

22.

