2.1 Study Hypotheses

2.1.5 **Primary hypothesis**: The overall Long COVID symptom severity score is lower after 4 weeks of once-per-week 23- to 60-hour water-only fasting [in addition to eating in an 8-

hour daily TRE window (16-hour water fasting) and following a low sugar diet] than after 4 weeks of 10- to 12-hour daily TRE (12- to 14-hour water fasting) and a low-sugar diet.

2.2.5 Secondary hypotheses:

- 2.2.1.5 The overall Long COVID symptom severity score is lower after 1, 2, or 3 weeks of once-per-week water-only fasting (in addition to eating in an 8-hour window daily and a low sugar diet) than after 1, 2, or 3 weeks of 10- to 12-hour daily time-restricted eating and a low-sugar diet.
- 2.2.2.5 The overall Long COVID symptom severity score is lower after the initial 2-week run-in phase of 10- to 12-hour daily TRE and a low-sugar diet reduces Long COVID symptom severity scores.
- 2.2.3.5 The count of Long COVID symptoms is lower after 1, 2, 3, or 4 weeks of onceper-week water-only fasting (in addition to eating in an 8-hour window daily and a low sugar diet) than after 1, 2, 3, or 4 weeks of 10- to 12-hour daily timerestricted eating and a low-sugar diet.

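### The SAP labels its analysis intent-to-treat, but includes people by available scores and compares treatments at week 4 on complete pairs only, with losses unstated

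*Combined protocol and SAP*

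**What the plan says.** SAP 4.0, Analysis Plan 3.1.5 opens with "The study population will be evaluated using an intent-to-treat approach to the statistical analysis" and continues with "All subjects who have data regarding symptom severity scores available at each time point will be included in the analyses". The second sentence can be read visit by visit, or as requiring a score at every visit. No missing-data method is given.

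The primary hypothesis (SAP 2.1.5) begins "The overall Long COVID symptom severity score is lower after 4 weeks of once-per-week" fasting and sets this against the score after four weeks of the TRE treatment. No test is labelled primary. The only planned test that compares the two treatments at a given week is in 3.3.5: "Symptom severity scores will be compared between the two study arms using the two-sided paired T-test at each time point, as appropriate". Item 3.4.5 adds a longitudinal model: "A repeated measures general linear model will be used to test differences between the two trial arms across baseline" and the ten weekly measurements that follow.

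The protocol (Study Procedures, step 20) says: "If a subject misses a key survey, then they are considered withdrawn from the study". The key surveys are the first and third baseline surveys, plus "the survey at the end of 4 weeks water fasting and the survey at the end of the relaxed time-restricted eating". Under step 21, for someone who leaves or no longer qualifies, "the subject will be removed, but the record will be maintained".

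On numbers, the synopsis gives a sample size of 96 (approval for 180). SAP 2.0 describes a trial population of 58, 29 randomised to each sequence, all of whom took part for 10 weeks. On timing, the Brief Summary puts randomisation after the two-week run-in, while Screening step 7 puts it on the screening call, before the run-in.

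**The concern.** Intent-to-treat keeps everyone randomised, in the sequence assigned. The rule in 3.1.5 depends instead on whether data exist, and the paired test narrows the set further to people who have both end-of-treatment scores. Those are the two on-treatment surveys whose absence triggers withdrawal under step 20. The kept record of a withdrawn participant may hold several on-treatment scores, but the paired test cannot use a record that lacks one member of the pair.

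What is at stake is both the label and the estimate. If people left because of how they responded to one treatment, the within-person difference among those remaining is not the difference for everyone randomised. SAP 5.0 acknowledges that the trial is open-label with self-reported symptoms, so loss related to response is plausible. Nothing in the documents shows that it happened.

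**Working it through.** **1. Which data each rule admits**

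| Rule | Who is in |
|---|---|
| Intent-to-treat label (3.1.5, first sentence) | everyone randomised |
| Inclusion rule (3.1.5, second sentence) | those with scores, per visit or at every visit |
| Week-4 paired t-test (3.3.5) | those with both end-of-treatment scores |
| Repeated measures model (3.4.5) | not stated |

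The rows agree only if every randomised person returned every survey that the rule in question needs. For the week-4 test, that means both end-of-treatment surveys.

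**2. Whether 3.4.5 settles it.** It does not, for two reasons. In the SAP's section on interventions an arm is a treatment, whereas in the synopsis an arm is a sequence, so the contrast depends on the reading and is not tied to week 4. The item also does not say whether an incomplete record is used or dropped.

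**3. Numbers lost.** SAP 2.0 gives 29 + 29 = 58; the synopsis gives 96. The difference is 96 − 58 = 38. The documents give no count of withdrawals, so the number lost cannot be derived. If the 58 are everyone randomised and all returned both endpoint surveys, it is zero.

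**4. Timing of randomisation.** If it took place on the screening call, people lost during the run-in belong in the intent-to-treat set. If it took place after the run-in, they do not. Such people have no on-treatment scores, so this affects the reported denominator more than the treatment estimate.

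**5. Size if there was loss (illustration).** From the documents: n = 58 analysed and a two-sided paired test. Assumed: a 5% level; no true mean effect over everyone randomised; a lost fraction p; and lost people whose fasting-minus-TRE difference would have averaged d SD worse than that of those kept. The SD is that of the paired differences in those kept.

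Let m be the mean difference in those kept. A zero overall effect requires (1 − p)m + p(m + d) = 0, so m = −p·d. The test statistic is then noncentral t with 57 df and noncentrality of size p·d·√58, where √58 = 7.616.

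| p | p × 0.5 × 7.616 | Rejects, d = 0.5 | Rejects, d = 0.25 |
|---|---|---|---|
| 0 | 0 | 5.0% | 5.0% |
| 0.10 | 0.381 | 6.6% | 5.4% |
| 0.20 | 0.762 | 11.6% | 6.6% |
| 0.30 | 1.142 | 20.2% | 8.7% |

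The rates are the same if the lost would have done better on fasting by the same amount; the false positives would then mostly favour TRE.

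**6. Tipping point.** A just-significant result has a mean of 2.0025/7.616 = 0.263 SD, where 2.0025 is the 97.5% point of t with 57 df. It becomes zero over everyone randomised if the lost were worse than those kept by 0.263/p: 2.63, 1.31 or 0.88 SD at 10%, 20% or 30% loss. These values are on the same scale as d, so a d of 0.5 would not overturn such a result at any of the three loss levels.

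**The case against.** The strongest reply is that SAP 2.0 plainly describes 58 people as randomised and says all of them took part for 10 weeks. On that reading nobody was lost, 96 was a target, and the shortfall is under-recruitment, which fits the limited sample size admitted in SAP 5.0. The paired test would then use everyone and the label would be right. This reading is possible and may be correct. But the wording would also fit a description of completers only, taking part for 10 weeks is not the same as returning both endpoint surveys, and no count of losses settles it.

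It is also fair to say that 3.1.5 does give an inclusion rule. The defect is that the rule conflicts with the label, not that a rule is absent. Step 20 says withdrawn, not excluded from analysis, and step 21 keeps the record. That stands, but it does not help a paired test.

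A reader might go further and infer that 38 randomised people were lost. Nothing says that 96 were randomised, and 38 is not an upper limit either: approval for 180 would by the same subtraction give 180 − 58 = 122.

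Finally, making a mixed model the intent-to-treat estimate, probably after data collection, introduces a late choice. That is a real cost, and is why disclosure is part of the fix.

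**Conclusion.** The point holds conditionally. As written, the SAP attaches an intent-to-treat label to an inclusion rule based on available data and to a week-4 test that can use only complete pairs. If any randomised participant lacks an endpoint, the label is wrong, and the estimate is biased if loss relates to response. If the 58 are everyone randomised and all returned both endpoints, the week-4 comparison is neither mislabelled nor biased in this way. The documents do not say which applies.

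A reader might infer that any bias must favour fasting, because people who felt worse while fasting would leave. The documents do not support a direction: they give no data on loss, and step 20 applies equally to the end-of-TRE survey.

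The size depends on assumed loss and an assumed difference between lost and kept. In the illustration a 5% test rejects between 5.4% and 20.2% of the time over 10% to 30% loss and 0.25 to 0.5 SD; small loss matters little. The wording conflict itself is certain and should be fixed; the harm to the estimate is not established.

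**What to change.** 1. Reconcile the Brief Summary with Screening step 7 on when randomisation took place. In SAP 2.0 and 3.1.5, define the intent-to-treat set as everyone randomised, in the assigned sequence.
2. Report numbers randomised, lost and analysed by sequence and period, and explain 96 against 58. If all 58 prove to be everyone randomised with both endpoints, this table settles the question.
3. Specify the 3.4.5 model as a likelihood-based mixed model with treatment, period, sequence and week (including treatment-by-week, so that week 4 can be read off) and participant random effects. Use every recorded weekly score, including those of withdrawn participants where their data may be used. Report its week-4 fasting-minus-TRE contrast as the intent-to-treat estimate. Disclose when the change was made and whether treatment comparisons had already been seen.
4. Label the paired t-test a complete-pairs analysis and report it beside the model.
5. If any endpoint is missing, add a missing-not-at-random tipping-point analysis, because the model in step 3 assumes missing at random.

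The cost is SAP wording, a flow table and model code on scores already in REDCap; no new data are needed. The downsides are a little more analysis work, reliance on missing at random, and a change that probably comes after data collection. The SAP describes data collection in the past tense, and the synopsis schedules the last recruit for April 2023, against a document date of 7/21/2023.

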DIET AND FASTING FOR LONG COVID; A CROSSOVER TRIAL

7/21/2023

NCT06214455

Trial Protocol and Statistical Analysis Plan

- Trial Protocol
- Statistical Analysis Plan (page 11)

Clinical trial protocol

SYNOPSIS

TITLE	Diet and Fasting for Long COVID
RESPONSIBILITY	[name]
	Principal Investigator
	Pacific Northwest University - Health Sciences
	College of Medicine, Department of biomedical Sciences
	[name]
	[name]
	Co-Principal Investigator
	Unaffiliated Patient Researcher
	[name]
STUDY CENTER	Pacific Northwest University - Health Sciences
	College of Medicine, Department of Biomedical Sciences
	[name]
PRIMARY OBJECTIVE	Change in Long COVID Symptom Severity Scores and Symptoms during Treatment A (diet, not-fasting) vs Treatment B (diet, fasting).
STUDY DESIGN	Interventional, randomized, all remote, two-arm crossover study, not blinded
STUDY ARMS	Experimental: Arm AB (Diet then Diet and Fasting)
	1. 2 week baseline with a low sugar diet and 10-12 hour eating window
	2. Treatment A: Eat a low sugar diet, 10-12 hour eating window for four weeks

	3. Treatment B: Eat a low sugar diet, 8 hour eating window, 23 to 60 hour fast once a week for four weeks
	Experimental: Arm BA (Diet and Fasting then Diet)
	1. 2 week baseline with a low sugar diet and 10-12 hour eating window
	2. Treatment B: Eat a low sugar diet, 8 hour eating window, 23 to 60 hour fast once a week for four weeks
	3. Treatment A: Eat a low sugar diet, 10-12 hour eating window for four weeks
SAMPLE SIZE	96 Long Covid subjects (approved for 180)
INCLUSION CRITERIA	Adult (18-69 years old)
	Five or more common Long Covid symptoms
	 Free from fever > 100F and known bacterial and parasitic infections
	 Must indicate willingness to limit certain supplements and report all medications.
	 Must indicate willingness to make significant dietary changes - and limit daily eating to an 8 or 10 hour window.
	 Must indicate willingness to attempt 36 hr or 60 hr water fasts each week for 4 weeks.
	Have a valid email address and phone number
	Reside in the United States
	Be able to read and to communicate in English

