3.0 Outcomes, Exposures, and Other Variables

1.1 Trial Intervention and Control Arms

- 1.1.5 Active "Control" Arm: a low-sugar diet with a 10- to 12-hour daily TRE eating window and water-only fasting for the other daily 12 to 14 consecutive hours.
- 1.2.5 Intervention Arm: a low-sugar diet with a more restrictive 8-hour daily TRE eating window and 16 consecutive hours of daily fasting, along with a once-weekly 23- to 60-hour water-only fast.

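### The crossover's fasting-versus-TRE contrast has only a paired t-test without a period term, and for the co-primary symptom count no such contrast is named

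*Combined protocol and SAP*

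**What the plan says.** The synopsis describes a randomised two-sequence crossover: two weeks of run-in, then four weeks on each treatment. End of period 1 is therefore week 6 and end of period 2 is week 10. The primary hypothesis (SAP 2.1.5) is that "The overall Long COVID symptom severity score is lower after 4 weeks of once-per-week 23- to 60-hour water-only fasting" than after four weeks of the less restrictive TRE regimen. The primary endpoints (SAP 3.0, 2.1.5) are two: a composite severity score over 60 symptoms and a count of those symptoms present.

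The analysis plan (SAP 4.0, section 3.1) has two provisions that bear on this contrast:

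- 3.3.5: "Symptom severity scores will be compared between the two study arms using the two-sided paired T-test at each time point, as appropriate". Similar comparisons follow for treatment weeks 1 to 3.
- 3.4.5: "A repeated measures general linear model will be used to test differences between the two trial arms across baseline and the 10 end-of-week measurements", for both LC-score and numLCsym.

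The t-tests in 3.4.5 compare baseline with the end of run-in and with the final week in all participants. Those in 3.9.5 are for subgroups. Neither compares fasting with TRE.

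The word *arm* changes meaning. SAP 3.0 uses it for a treatment ("Intervention Arm: a low-sugar diet with a more restrictive 8-hour daily TRE eating window"), as does 3.3.5 ("balanced between the TRE arm and the Fasting arm of the study"). The synopsis uses it for a sequence ("Experimental: Arm AB (Diet then Diet and Fasting"). Protocol step 18 merges the two: "Treatment group A, 'TRE then Fasting', has a low sugar diet and a 10-12 hour eating window".

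On who is analysed, SAP 3.1.5 says "All subjects who have data regarding symptom severity scores available at each time point will be included in the analyses". SAP 2.0 gives 58 participants, 29 per sequence, and says that all took part for 10 weeks.

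**The concern.** A paired t-test on fasting minus TRE treats every participant's difference as a draw from one distribution. In an AB/BA design, any change common to everyone between week 6 and week 10 adds to the difference in one sequence and subtracts from it in the other. Without a period term, that drift is counted as random error. Drift is plausible on the plan's own terms, because the protocol's study hypothesis expects the diet and TRE themselves to reduce symptoms, and the diet is common to both treatments. SAP 5.0 already lists small sample size as a limitation, so avoidable loss of power matters.

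The second issue is coverage. Section 3.3.5 speaks only of severity scores. For the symptom count, the reader has only the 3.4.5 model, and it does not say which term answers the primary question. The 3.4.5 result cannot be read as a fasting effect until that term is named.

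**Working it through.** **1. What *arm* can mean in each test.** A paired test needs both values from the same person, so in 3.3.5 *arm* must be treatment. Over baseline, run-in and both periods, participants can be divided only by sequence, so in 3.4.5 *arm* must be sequence.

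**2. What the 3.4.5 model yields.** Each sequence has 4 of its 11 measurements on fasting, so a constant fasting effect contributes 4/11 − 4/11 = 0 to the arm main effect. Example: fasting effect −5 and drift −3 (arbitrary units).

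- AB is 0 at week 6 and −8 at week 10. BA is −5 at week 6 and −3 at week 10.
- With constant effects within periods, both sequence means over 11 time points are −32/11, so the main effect is 0.
- The contrast ½[(−8 − 0) − (−3 − (−5))] = ½(−8 − 2) = −5 recovers the effect free of drift. It is estimable from arm-by-time, but the plan does not name it.

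**3. What omitting the period costs in 3.3.5.** The documents give no SD, effect size or drift, so these are assumptions. Let the within-person difference (fasting minus TRE) have SD 1 within sequence, effect size τ = 0.374 (about 80% power at 29/29 without drift) and drift π. The mean difference is τ + π in AB and τ − π in BA.

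- Paired SE relative to period-adjusted SE = √(1 + π² × 58/57).
- Equivalent N = 58 / ratio².
- Paired power and type I error: mean difference normal with variance 1/58, and sum of squares noncentral chi-square (57 df, noncentrality 58π²), integrated numerically.
- Period-adjusted power: noncentral t, 56 df, noncentrality 0.374 × √58.

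| Drift (SD) | SE ratio | Equivalent N | Paired power | Adjusted power | Paired type I error |
|---|---|---|---|---|---|
| 0.1 | 1.005 | 57.4 | 79.7% | 79.9% | 4.9% |
| 0.25 | 1.031 | 54.5 | 78.2% | 79.9% | 4.3% |
| 0.5 | 1.120 | 46.2 | 72.7% | 79.9% | 2.9% |
| 1.0 | 1.420 | 28.7 | 50.5% | 79.9% | 0.6% |

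With no drift, paired power is 79.96% and adjusted power 79.93%, so the adjustment costs 0.03 percentage points.

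**4. Bias.** Bias of the paired estimate = π(nAB − nBA)/N. At 29/29 it is 0. At 29/28 it is π/57 = 0.018π. Larger imbalances are assumed cases. By simulation at drift 0.5 SD, paired type I error is 3.9% at 32/26, 6.5% at 34/24 and 15.7% at 38/20.

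**5. Carryover.** If a fraction c of the fasting effect persisted to TRE week 4 in BA, the paired (29/29) and period-adjusted estimates would both become τ(1 − c/2). For assumed c = 0.25 and 0.5 they shrink by 12.5% and 25%, and adjusted power falls to 69% and 56%. A comparison at week 6 alone, adjusted for week 2, has effect 0.374√(2(1 − r)) and SE √((1 − r²) × 2/29) on 55 df. Its power is 37%, 33% and 30% at assumed score correlations r of 0.5, 0.7 and 0.9.

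**The case against.** The strongest reply is that the power loss rests on a drift no document supports. It becomes sizeable only near 0.5 SD, which exceeds the assumed treatment effect and would have to arise after a two-week run-in and a full treatment period. With drift equal to the effect (0.374 SD), paired power is 75.9%, a loss of about 4 points. This stands: taken alone, the missing period term is a modest efficiency point.

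A reader might infer that the paired test is biased or could produce a false-positive fasting result. The documents do not support that. At 29/29 it is unbiased absent carryover, and conservative. Unequal counts are unlikely within the 58, since SAP 2.0 says all took part for 10 weeks and protocol step 20 treats the end-of-fasting and end-of-TRE surveys as key, with a missed one meaning withdrawal. They are not excluded in a wider set, because the synopsis figure of 96 is not reconciled with 58. Even then, modest imbalance need not inflate type I error, as the 32/26 case shows.

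A reader might also infer that the plan has no model able to adjust for period, or that carryover would stay invisible. Both go too far. A sequence-by-time version of 3.4.5 contains the period-adjusted contrast, and its data for weeks 3–6 and 7–10 could show carryover. What remains is that neither the contrast nor any carryover check is named.

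**Conclusion.** The point holds as a gap in specification and efficiency; it does not make the planned analysis invalid. For severity scores, the named test omits the period term that the crossover design calls for. For the co-primary symptom count, no fasting-versus-TRE test is named at all, and this is the firmer part because it rests on the text alone.

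The size of the power loss is unknown. Under the assumptions above it is negligible at drift of 0.1 SD, under 2 points at 0.25 SD, about 7 points at 0.5 SD and about 29 points at 1.0 SD. Bias requires unequal analysed sequences, and carryover is a possibility that the documents neither show nor exclude. Because the remedy uses existing data and costs almost nothing, it should be made.

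**What to change.** - **Terms.** Use *sequence* for AB/BA and *treatment* for fasting/TRE throughout.
- **Primary test, for both LC-score and numLCsym.** For each participant take the week-10 minus week-6 difference, compare it between sequences with a two-sample t-test, and report half the AB-minus-BA difference, which is fasting minus TRE, with its 95% CI. Use the same form for treatment weeks 1 to 3.
- **The 3.4.5 model, if kept.** Make it secondary, with time (period) in the model, and name fasting minus TRE at treatment week 4 as the tested contrast. State how the baseline and run-in weeks enter: either leave them out of the treatment and period coding, or use them as baseline covariates.
- **Optional.** Report the week-6 score by sequence, adjusted for the week-2 score, as a carryover sensitivity analysis. Period adjustment does not remove carryover. At 30–37% power, this check can support the main result but not replace it.
- **Separately.** Reconcile the Brief Summary's five-day washout with the differing fast lengths in the documents (23 to 60 hours in the synopsis arms and SAP; 36 or 60 hours in the protocol steps). Time left in the week is 7 days minus the fast: 4.5 days after 60 hours, 5.5 after 36 and about 6.0 after 23. In each case it falls inside the Treatment B week.

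The cost is SAP wording, R code and one degree of freedom (0.03 percentage points of power if there is no drift); no new data are needed. If the data have already been examined, the change must be dated and disclosed, and the paired result shown beside the new one.

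### The SAP does not say how the 11-occasion model treats missed non-key surveys; in its conventional form it would drop participants whom the protocol appears to retain

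*Combined protocol and SAP*

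**What the plan says.** **The model.** SAP 4.0, 3.1 Analysis Plan, item 3.4.5 plans a repeated measures general linear model to "test differences between the two trial arms across baseline and the 10 end-of-week measurements of the LC-score and numLCsym", which is 11 occasions. The SAP does not define the two short names. They appear to be the two primary endpoints in SAP 3.0, 2.1.5 (total severity and symptom count). The SAP gives no covariance structure, estimation method or rule for missing occasions. On software, item 3.7.5 says only "Analyses will use R Studio".

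**Who is analysed.** Item 3.1.5 claims an intent-to-treat approach and continues: "All subjects who have data regarding symptom severity scores available at each time point will be included in the analyses".

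**Who is retained.** Protocol, Study Procedures, step 20 says: "If a subject misses a key survey, then they are considered withdrawn from the study". The key surveys are "The first and third baseline surveys, the survey at the end of 4 weeks water fasting and the survey at the end" of the 10-to-12-hour eating period. Step 20 states no consequence for missing any other survey.

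**The concern.** The retention rule and the model do not obviously fit together. Step 20 protects four occasions, while the model spans 11. The usual wide-format repeated measures general linear model deletes a person who lacks a single occasion. An analyst who takes that form, and reads 3.1.5 as requiring a score at every time point, would exclude people who met every survey requirement that carries a stated consequence.

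Two things are at stake. The first is precision in a planned test of what appear to be both primary measures. SAP 2.0 already puts the population at 29 per sequence, against the 40 to 90 per arm in the SAP's Power Calculation. The second is the assumption behind the result. Listwise deletion needs missed surveys to be missing completely at random, and that is hard to take for granted with self-reported symptoms in an open-label trial. The model and the week-4 paired test could also describe different sets of people. Finally, the choice between complete-case and available-data fitting would be left until after the data are seen.

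**Working it through.** **1. Count the surveys.** Step 17 places baseline surveys at weeks 0, 1 and 2. The eight treatment weeks add weeks 3 to 10. Total 3 + 8 = 11, which agrees with 3.4.5.

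Key surveys: the first baseline is week 0 and the third is week 2. The two four-week treatments end at weeks 6 and 10, in either sequence. Non-key surveys: 11 − 4 = 7 (weeks 1, 3, 4, 5, 7, 8 and 9).

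**2. What each analysis needs.**
- The primary hypothesis (SAP 2.1.5) compares scores after four weeks of each treatment. Both surveys are key, so a missed non-key survey costs that comparison nobody.
- The comparisons at week 1, 2 or 3 of each treatment each need two non-key surveys.
- The conventional form of the 3.4.5 model needs all seven non-key surveys as well as the four key ones.

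**3. Size if the model is fitted to complete cases.** The documents give no miss rate, so the rate m per non-key survey is an assumption. With independent misses, the share complete is P = (1 − m)^7, the number left is 58 × P, and the standard error is multiplied by 1/√P. A model using all observed scores keeps all 58 people and (4 + 7(1 − m))/11 of the measurements.

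| m | P | Left of 58 | SE factor | Measurements kept with all observed data |
|---|---|---|---|---|
| 2% | 0.868 | 50.4 | 1.07 | 98.7% |
| 5% | 0.698 | 40.5 | 1.20 | 96.8% |
| 10% | 0.478 | 27.7 | 1.45 | 93.6% |

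For contrast, a week 1, 2 or 3 paired comparison at m = 5% keeps 0.95² × 58 = 52.3 people.

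**4. If misses cluster within people.** Independence is the harsh case. Under a beta-binomial model with within-person correlation ρ, set a = m(1/ρ − 1) and b = (1 − m)(1/ρ − 1). Then P is the product over i = 0 to 6 of (b + i)/(a + b + i).

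| m | ρ = 0.1 | ρ = 0.3 | ρ = 0.5 |
|---|---|---|---|
| 2% | 52.0 | 53.9 | 55.1 |
| 5% | 44.0 | 48.2 | 50.8 |
| 10% | 33.0 | 39.8 | 44.4 |

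Entries are people left of 58.

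**5. Sensitivity to the survey count.** The protocol's Brief Summary lists run-in surveys only at weeks 0 and 2, while step 17 adds week 1. Without week 1 there would be six non-key surveys. At 2%, 5% and 10%, 58 × (1 − m)^6 gives 51.4, 42.6 and 30.8. The conclusion does not change, but the two passages should be reconciled.

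**The case against.** The strongest reply is that the documents nowhere require all 11 scores. A reader might infer from the model's name that anyone with a gap cannot be analysed. The SAP does not say so, and R can fit a linear model for repeated measures to every available row by generalised least squares or as a mixed model. This stands: the loss is conditional on how the model is fitted. It also shows the gap, because the present text permits either fit.

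It can also be said that 3.1.5 already covers these people. On one reading, whoever has a score at a given time point is included there. On the other, only those with scores at every time point are included. The sentence supports both, so it does not settle the matter and has to be part of the repair.

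Other limits also stand:
- A reader might infer that this is the trial's only comparison over time. It is not. 3.3.5 plans comparisons at weeks 1 to 3 of each treatment, and 3.4.5 tests baseline against week 2 and against the final week. It is the only model across all time points.
- Retention after a non-key miss is inferred from step 20's silence.
- Nothing shows that any of the 58 missed a survey. Step 20 provides reminders, SAP 4.0, 1.1.5 promises close contact with participants, and SAP 2.0 says all took part for 10 weeks.
- A reader might infer that people skip surveys in bad weeks, so that complete cases look too well. The documents give no evidence for this direction. If it were so, the mixed model would not remove that bias either.

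**Conclusion.** The point holds as a gap in specification. A participant who misses one of seven non-key surveys appears to remain in the trial, yet could be dropped from the only model spanning all 11 occasions. Neither 3.4.5 nor 3.1.5 rules this out.

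If the model is fitted to complete cases, the loss could range from modest to large. About 50, 41 or 28 of 58 would remain at independent miss rates of 2%, 5% or 10%. With within-person correlation of 0.1 to 0.5, about 44 to 51 would remain at 5% and 33 to 44 at 10%. All of these rest on assumed rates. The documents do not show that participants were in fact lost or that the result is biased. The primary week-4 comparison is untouched, so this is a worthwhile and cheap correction to a supporting analysis.

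**What to change.** 1. **SAP 3.4.5:** replace the repeated measures general linear model with a linear mixed model fitted by REML to every observed weekly score. Pre-specify one parsimonious within-person covariance, for example a random person intercept with AR(1) errors. Do not use an unstructured matrix: 11 occasions need 11 × 12/2 = 66 parameters, against 58 people.
2. **SAP 3.1.5:** state that a participant is included with whatever weekly scores are observed. Changing 3.4.5 alone would leave the complete-case reading of 3.1.5 in place.
3. **Reporting:** give the number of scores observed at each week.

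The cost is two revised SAP sentences, one reporting line and the matching R code. No new data or change in trial conduct is needed. The downside is reliance on missing-at-random. That is weaker than the missing-completely-at-random assumption needed for listwise deletion, but it does not remove bias if skipping depends on that week's unobserved severity.
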